12.1.2. Exposure vs. Dose

CC-122 and Nivolumab plasma concentrations will be summarized by phase, actual dose level (CC-122), visit, and nominal time points. Plasma PK parameters will be summarized by phase, actual dose level (CC-122) using descriptive statistics (N, mean, standard deviation, coefficient of variation [CV%], geometric mean, geometric CV%, median, min, and max). In general, geometric mean and the geometric CV (%) will be derived from non-zero concentration values.

Coefficient of variation CV (%) is calculated as follows: $100 \times (\text{standard deviation} / \text{mean})$.

Geometric CV (%) is calculated as follows: $CV (\%) = 100 \times \sqrt{\exp(\hat{\sigma}^2) - 1}$, where $\hat{\sigma}^2$ denotes the variance of the log-transformed values.

The following figures will be provided by actual CC-122 dose levels:

- Individual subject's concentration (linear scale) over time spaghetti plot;
- Individual subject's concentration (semi-logarithmic scale) over time spaghetti plot;
- Mean and \pm standard deviation of concentration (linear scale) over time plot;
- Mean and \pm standard deviation of concentration (semi-logarithmic scale) over time plot.

In addition, scatter plots of log transformed AUC_t , AUC_∞ , and C_{max} versus CC-122 dose will be presented.

12.1.3. Exposure vs. Efficacy and/or Safety Parameters

Analyses will be performed to assess the exposure-response relationship of CC-122 plasma exposure (e.g. C_{max} , and AUC) with key efficacy parameters (tumor burden reduction and tumor shrinkage). Graphical analyses of the data will be conducted to visualize potential trends between drug exposure and response.

[REDACTED]

- [REDACTED]
- [REDACTED]

[REDACTED]

[REDACTED]

[REDACTED]

[REDACTED]

[REDACTED]

[REDACTED]

[REDACTED]

12.3. Adjustment of Multiplicity

Not applicable for this study.

13. QUALITY OF LIFE ANALYSIS

Not applicable for this study.

14. INTERIM ANALYSIS

No formal interim analysis is planned.

15. CHANGES TO THE STATISTICAL ANALYSES SECTION OF THE PROTOCOL

1. The protocol defines “enrolled population” as “All subjects who meet all the inclusion/exclusion criterion and are eligible for the study.” As written, this definition excludes those subjects who were enrolled into the study and later discovered to have not met an inclusion/ or met an exclusion criteria. In order to accurately reflect ALL subjects who were enrolled into the study, the definition of enrolled population is expanded to remove the inclusion/exclusion criteria caveat which include all subjects who were assigned an enrollment number. The enrolled subjects who did not meet inclusion/exclusion criteria will be captured as protocol violators, which will be reported separately in a listing of protocol violations.
2. Per study HODC (Hematology and Oncology Development Committee) decision, this study will not be moving into expansion phase, thus the analyses described in the protocol for expansion phase as well as the exploratory efficacy analyses limited by the data will not be performed.
3. The following exploratory objectives, originally described in the study protocol, are not considered in this SAP and will be described in separate reports, if applicable.
 - To determine the relationship between baseline gene expression profiling, deoxyribonucleic acid (DNA) mutations, T cell clonality and protein biomarker expression with clinical endpoints including tumor response, response duration and progression free survival (PFS)
 - To determine the relationship of CC-122 and Nivolumab pharmacodynamics (PD) biomarkers in peripheral blood and changes in immune markers in tumor to clinical endpoints including tumor response, response duration and PFS
 - To determine the relationship between the plasma concentrations of CC-122 and Nivolumab and [REDACTED]s, safety, and clinical endpointsTherefore, the corresponding analyses including the analysis [REDACTED] described in Section 9.9 of the protocol are not considered in this SAP.

4. Futility analysis is no longer planned in this study.
5. Shift tables for vital signs and LVRF are no longer needed in this study.
6. Treated Population has been changed to Safety Population. This change was made because regulatory guidance provides a definition for Safety Population (all patients who took at least 1 dose of study medication; [REDACTED]), which represents the same subject population in the CC-122-HCC-002 protocol named as the “Treated Population” (ie, all subjects who enroll and take at least one dose of either IP [CC-122 or nivolumab]). Food

and Drug Administration (FDA). Guidance for industry: Submitting Select Clinical Trial Data Sets for Drugs Intended To Treat Human Immunodeficiency Virus-1 Infection. Mar 2018.

7. Correlation analyses will no longer be performed.
8. A listing of AESIs will now be created along with the listing of AEs
9. Summary of number of subjects who overdose is added to section 9.

[REDACTED]

17. APPENDICES

17.1. Dose Escalation Rules

Table 10: Decision Rules for Rolling 6 Dose Escalation Design

Current Cohort Information			Enrolling Dose Level*		
No. Enrolled	No. with DLTs	No. Without DLT	No. Pending	MTD Not Exceeded	MTD Exceeded
2	0,1	Any	Any	n	
2	2	0	0	n-1	
3	0	0,1,2	3,2,1	n	
3	0	3	0	n+1	
3	1	0,1	2,1	n	
3	1	2	0	n	
3	≥2	Any	Any	n-1	
4	0	0,1,2	4,3,2	n	n
4	0	3	1	n	n
4	0	4	0	n+1	n
4	1	0,1	3,2	n	n
4	1	2	1	n	n
4	1	3	0	n	n
4	≥2	Any	Any	n-1	n-1
5	0	0,1,2	5,4,3	n	n
5	0	3,4	2,1	n	n
5	0	5	0	n+1	n
5	1	0,1	4,3	n	n
5	1	2	2	n	n
5	1	3,4	1,0	n	n
5	≥2	Any	Any	n-1	n-1
6	0	0,1,2	6,5,4	Suspend	Suspend
6	0	3,4	3,2	Suspend	Suspend
6	0	5,6	1,0	n+1	MTD**
6	1	0,1	5,4	Suspend	Suspend
6	1	2	3	Suspend	Suspend

Current Cohort Information			Enrolling Dose Level*		
No. Enrolled	No. with DLTs	No. Without DLT	No. Pending	MTD Not Exceeded	MTD Exceeded
6	1	3,4	2,1	Suspend	Suspend
6	1	5	0	n+1	MTD
6	≥2	Any	Any	n-1	n-1
* n is the current dose level of subjects enrolled; n+1 and n-1 represent dose level escalation and de-escalation, respectively. Enrollment will be suspended at where it is indicated.					
** MTD is claimed only when there are 6 evaluable subjects.					

17.2. Handling of Dates

Dates will be stored as numeric variables in the SAS analysis files and reported in DDMMYYYY format (i.e., the Date9. datetime format in SAS). Dates in the clinical database are classified into the categories of procedure dates, log dates, milestone dates, outcome dates, and special dates.

- **Procedure Dates** are the dates on which given protocol-specified procedure are performed. They include the dates of laboratory testing, physical examinations, tumor scans, etc. They should be present whenever data for a protocol-specified procedure are present and should only be missing when a procedure are marked as NOT DONE in the database. Procedure dates will not be imputed.
- **Log Dates** are dates recorded in CRF data logs. Specifically, they are the start and end dates for AEs and concomitant medications/procedures. They should not be missing unless an event or medication is marked as *ongoing* in the database. Otherwise, incomplete log dates will be imputed according to the rules in Appendix 17.4. However, in listings, log dates will be shown as recorded without imputation.
- **Milestone Dates** are dates of protocol milestones such as randomization, study drug start date, study drug termination date, study closure date, etc. They should not be missing if the milestone occurs for a subject. They will not be imputed.
- **Outcome Dates** are dates corresponding to study endpoints such as survival, progression, etc. In most cases they are derived either from a milestone (e.g., the survival date is derived from the death date), or a procedure date (e.g., the progression date is derived from the date of the tumor scan that was used to determine progression). They may be subject to endpoint-specific censoring rules if the outcome did not occur, but are not otherwise subject to imputation.
- **Special Dates** cannot be classified in any of the above categories and they include the date of birth. They may be subject to variable-specific censoring and imputation rules.

Dates recorded in comment fields will not be imputed or reported in any specific format.

17.2.1. Calculation Using Dates

Calculations using dates (e.g., PFS, subject's age or relative day after the first dose of study drug) will adhere to the following conventions:

- Study days after the start day of study drug will be calculated as the difference between the date of interest and the first date of dosing of study drug plus 1 day. The generalized calculation algorithm for relative day is the following:
 - If TARGET DATE \geq DSTART then STUDY DAY = (TARGET DATE – DSTART) + 1;
 - Else use STUDY DAY = TARGET DATE – DSTART.

Note that Study Day 1 is the first day of treatment of CC-122. Negative study days are reflective of observations obtained during the baseline/screening period. Note: Partial dates for the first study drug are not imputed in general. All effort should be made to avoid incomplete study drug start dates.

- Age (expressed in days) is calculated: AGE = CONSENT – DATE of BIRTH + 1. In practice, age will be transformed to years by dividing the difference by 365.25 days, then truncating.
 - Preference is for using calculated age from clinical database. When not available, calculated age from CRF or IVRS may be used
 - Partial birth date: impute missing day as 15th of the month; impute missing month as July; set missing age for missing year
- Intervals that are presented in weeks will be transformed from days to weeks by using (without truncation) the following conversion formula:
$$\text{WEEKS} = \text{DAYS} / 7$$
- Intervals that are presented in months will be transformed from days to months by using (without truncation) the following conversion formula:
$$\text{MONTHS} = \text{DAYS} / 30.4167$$

17.2.2. Calculation of Cycles

The start date of each cycle is defined as the date when the subject receives CC-122 if they receive CC-122; otherwise the first date they received Nivo will be the start date in that cycle. After the start dates are determined, the end date of each cycle is defined as (start date of subsequent cycle-1). The end date of the last cycle will be the dose start date of last cycle + 27.

17.3. Baseline, Repeated Measurements, and End of Trial

The general conventions for handling baseline, repeated measurements, and EOT are provided below:

- Baseline for any clinical laboratory test, vital sign and ECOG performance status is defined as the last value of a specific endpoint measured before first dose of the earliest of CC-122 or Nivolumab;

- Baseline values for biomarkers in the study is defined as the average of all qualified values (as specified in [Table 12](#) and [Table 13](#)) collected at screening and before first dose of the earliest of CC-122 or Nivolumab, including values from Cycle 1 Day 1 pre-dose (0 hr) and qualified unscheduled visits. Other pre-dose samples from on-treatment visits after the first dose of the IP will not be used to impute the study baseline value. In addition, for those biomarkers with measurements at multiple timepoints within a visit, the qualified pre-dose (0 hr) value will be used to calculate the change from pre-dose, percent of pre-dose and/or percent change from pre-dose for the post-dose time points from the same visit.
- When there are multiple values for any laboratory test (clinical) or vital sign collected at the same visit, the one with last/latest assessment time stamp will be used for data analysis.
- When there are multiple values for biomarker data collected at the same visit, the average will be used for data analysis.
- Baseline of ECG triplicate measurement is defined as the mean of the ECGs recorded prior to initiation of therapy. Hence the baseline ECG endpoint value is obtained by averaging the last 3 ECGs or whatever number is available before the first dose of study treatment (earliest of CC-122 or Nivolumab). If the ECG overall interpretation is different in the triplicate, the best value (i.e. the lowest one) at baseline and the worst value (i.e. the highest one) at post-baseline visits will be used in the shift tables. The overall interpretation is classified as (from lowest to highest) normal, abnormal not clinically significant and abnormal clinically significant.
- For repeat ECGs at a particular post-baseline visit, derive RR, QTcB, QTcF first for each measurement and then derive the average of heart rate, RR, PR, QRS, QT, QTcB, QTcF measurements from all repeat ECGs. The average will be used to compute the descriptive statistics for that visit and the worst value at that visit will be used in the shift tables.
- EOT assessment for a particular endpoint is defined as the last non-missing post-baseline assessment during the study period.

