11.2. Clinical Laboratory Evaluations

Clinical laboratory results of interest include: chemistry (including troponin T and BNP), hematology (including PT/INR/PTT), immunology, thyroid functions and urinalysis. Clinical laboratory values will be graded according to NCI CTCAE version 4.03 or higher for applicable tests. Book or literature normal ranges will be used to determine the categories of High, Low, and Normal.

Lab results and change from baseline will be summarized by visit using descriptive statistics for continuous variables. Similarly, maximum and minimum post-baseline values and corresponding change from baseline values (including unscheduled visits) will be summarized using descriptive statistics.

Shift tables demonstrating the changes (low/normal/high) from baseline to worst post-baseline value will be displayed in cross-tabulations for categorical variables. Bidirectional shift tables (low and high) demonstrating the change of NCI CTCAE grades from baseline to worst post-baseline during the treatment period will also be presented. These will be presented in separate tables for low and high NCI CTCAE grades. Summaries of worst NCI CTCAE grade by cycle (up to and including cycle 6) and worst post-baseline NCI CTCAE grade will be provided.

Listings of clinical laboratory data with NCI CTCAE grades (if applicable) and abnormal flags (low or high) will be provided.

Listing of pregnancy status will be also provided.

For some key lab tests, spaghetti plots for individual subjects will be presented to show the pattern of the lab test values over time using the Safety Population. All non-missing lab test values including assessments at scheduled and unscheduled visits will be presented. The x-axis will be the scheduled visits, and the y-axis will be the exact values (unscheduled results will be associated with the scheduled visit they relate to). Value for the EOT visit will be included in spaghetti plots but will be displayed for the nominal visit equal to or immediately after the EOT visit. The mean plot lab test values for each dose cohort in the dose escalation part and for each subgroup in dose expansion part will also be provided.

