11.3. Vital Sign Measurements

Vital sign values and change from baseline will be summarized using descriptive statistics for each visit. Similarly, maximum and minimum post-baseline values and corresponding change from baseline values (including unscheduled visits) will be summarized using descriptive statistics.

Shift tables demonstrating the changes (low/normal/high) from baseline to worst post-baseline value will be displayed in cross-tabulations. Normal ranges in [Table 9](#) will be used to determine the categories of low, normal and high. A listing of vital sign results will be provided.

Table 9: Normal Ranges of Vital Sign Measurements

Test	Normal Range (Unit)
DBP	[60, 90] (mmHg)
SBP	[100, 140] (mmHg)
Pulse	[60, 100] (bpm)
Temperature	[35, 38] (°C)

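### The last-value rule in SAP 17.3 can drop the worst laboratory or vital-sign value from worst-value outputs, and its best-at-baseline, worst-afterwards ECG rule tilts the shift table towards worsening

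*SAP*

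**What the plan says.** **Laboratory tests and vital signs.** SAP 17.3 sets general conventions for repeated measurements. With several values at one visit, "the one with last/latest assessment time stamp will be used for data analysis". No output is exempted. SAP 17.5 uses the term data analysis to mean tables and figures, and keeps original laboratory data in the listings.

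SAP 11.2 plans laboratory outputs that need the worst value:
- shift tables "from baseline to worst post-baseline value will be displayed in cross-tabulations for categorical variables";
- CTCAE outputs: "Summaries of worst NCI CTCAE grade by cycle (up to and including cycle 6) and worst post-baseline NCI CTCAE grade will be provided";
- maximum and minimum post-baseline values, with unscheduled visits included.

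Protocol 9.7 also plans shifts to the worst post-baseline grade. For vital signs, SAP 11.3 says "maximum and minimum post-baseline values and corresponding change from baseline values (including unscheduled visits) will be summarized". It still describes a shift table too, but SAP section 15, item 5 withdraws it: "Shift tables for vital signs and LVRF are no longer needed in this study".

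**ECG.** If the overall interpretations within a triplicate differ, SAP 17.3 says that for the shift tables "the best value (i.e. the lowest one) at baseline and the worst value (i.e. the highest one) at post-baseline visits will be used". SAP 11.4 plans that shift table, and section 15 does not withdraw it. Numeric ECG parameters are averaged at baseline and at each visit for descriptive statistics.

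**The concern.** A last-value rule suits a by-visit mean, where each subject should contribute one number. It does not suit a table whose purpose is to show the worst value recorded. If an abnormal result is followed by a milder one under the same visit label, the literal rule removes the abnormal result before the worst is taken. SAP 11.2 brings in unscheduled visits, but only in the maximum/minimum sentence, and nothing in the SAP restores an earlier value from the same visit.

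The ECG rule errs in the other direction. A subject read normal, abnormal, normal before dosing and again afterwards is counted as normal at baseline and abnormal after it. There is no control arm to subtract this from (SAP 4.3), and the study did not go on to expansion (SAP section 15, item 2). The tables therefore describe small escalation cohorts. In a cohort of six, one spurious shift is 1/6, about 17%.

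**Working it through.** The documents give no figure on this point, so there is none to reproduce. The only design input is three recordings per ECG time point (Protocol 6.7). The abnormal-reading rate, the correlations and the repeat rates below are assumptions.

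**1. Laboratory: which rule governs.** SAP 17.3 covers any clinical laboratory test or vital sign and exempts nothing. SAP 11.2 asks for worst values and does not mention same-visit repeats. Neither section says which prevails, and section 15 lists no change to the worst-grade tables planned in Protocol 9.7.

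**2. Laboratory: possible loss.** Suppose a visit holds two values, each out of range with probability p, and the two indicators have correlation ρ.
- P(both) = p² + ρp(1−p)
- P(any) = 2p − P(both)
- Share of visits with an exceedance that the last value misses = (P(any) − p) / P(any)

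| p = 0.10 | P(both) | P(any) | Missed share |
|---|---|---|---|
| ρ = 0 | 0.010 | 0.190 | 0.090/0.190 = 47% |
| ρ = 0.5 | 0.055 | 0.145 | 0.045/0.145 = 31% |
| ρ = 0.8 | 0.082 | 0.118 | 0.018/0.118 = 15% |

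Nothing is lost at a visit with one value. If only a fraction f of visits hold two values, the missed share overall is f(P(any) − p) / [f·P(any) + (1−f)p]. At ρ = 0.5:
- f = 0.05: 0.00225/0.10225 = 2.2%
- f = 0.20: 0.009/0.109 = 8.3%
- f = 1: 31%

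If instead only abnormal first values are repeated, and a fraction g of them are repeated within the visit, the share lost is g(1−p)(1−ρ). At ρ = 0.5 this is 0.45g, for example 4.5% at g = 0.10. These are losses per visit. A worst-over-study table loses less, because another visit may carry an equally bad value.

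**3. ECG: one post-baseline visit, no true change.** Each tracing is read abnormal with probability p. With independent tracings:
- SAP rule, shift up: (1 − p³)[1 − (1−p)³]; shift down: p³(1−p)³
- Worst of three at both times, each direction: (1−p)³[1 − (1−p)³]

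| p | SAP rule up | SAP rule down | Worst/worst, each way |
|---|---|---|---|
| 0.05 | 14.3% | 0.01% | 12.2% |
| 0.10 | 0.999 × 0.271 = 27.1% | 0.001 × 0.729 = 0.07% | 0.729 × 0.271 = 19.8% |
| 0.20 | 48.4% | 0.4% | 25.0% |

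A majority reading at both times gives P(abnormal) = 3p²(1−p) + p³ = 0.028 at p = 0.10, so 0.028 × 0.972 = 2.7% each way.

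**4. ECG: correlated tracings.** Let each subject's own p follow a beta distribution with mean 0.10.

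| Intraclass correlation | SAP rule up | SAP rule down | Worst/worst, each way |
|---|---|---|---|
| 0.3 | 19.1% | 0.21% | 8.6% |
| 0.6 | 10.9% | 0.13% | 3.7% |
| 0.8 | 5.5% | 0.06% | 1.6% |

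**5. ECG: worst over several visits.** With four visits, p = 0.10 and independence, the SAP rule gives 71.7% up. Worst/worst still gives 52.3% up against 7.7% down. A symmetric triplicate rule therefore removes only the part of the tilt that comes from the triplicate rule.

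**The case against.** **The laboratory loss is not certain.** A reader might infer that the worst-value tables will miss the worst value. The documents do not support that. SAP 17.3 is a general convention, and the more specific request in SAP 11.2 for worst values could be taken to override it. Most repeats that the protocol specifies also fall on other days: weekly troponin-T, BNP and ECG checks, blood counts after 24 to 48 hours, and liver tests twice weekly. Recorded as unscheduled visits, these enter the maximum/minimum summaries. SAP 11.2 does say that "unscheduled results will be associated with the scheduled visit they relate to", but only for the plot axis, so it does not show that unscheduled values are merged into a scheduled visit elsewhere. What stands is that the literal rule and the planned tables conflict, and a programmer must choose between them.

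**Large laboratory percentages need an assumption the documents do not give.** High losses follow if every abnormal value is repeated at the same visit. Neither document states how often that happens, or that repeats are usually prompted by an abnormal first result.

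**The vital-sign shift table is not at risk.** SAP 11.3 still describes it, but section 15 withdraws it. Only the maximum/minimum summaries remain exposed.

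**The ECG rule can be defended as a conservative safety choice.** Best baseline against worst afterwards gives the greatest sensitivity to worsening. Worst of three at baseline can hide real worsening: at p = 0.10 with independent tracings, 27.1% of subjects would start as abnormal by noise. The tracings are also minutes apart, so the independent-tracing figures are probably too high. These points bear on size and on the choice of remedy. They do not remove the one-directional tilt.

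**Neither rule touches the primary endpoint or dosing.** A reader might infer otherwise, because toxicity is the Phase 1 primary endpoint. That endpoint is DLTs and TEAEs. A laboratory abnormality becomes an AE under the investigator criteria of Protocol 10.3, DLTs have their own table (SAP 11.1.2), and the Safety Review Committee reviews all available data.

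**Conclusion.** The point holds in a limited form. For laboratory data and the vital-sign maximum/minimum summaries, SAP 17.3 as written can exclude the worst recorded value from outputs meant to show it. The condition is several values at one visit with the last not the worst. No size can be fixed: at a 10% exceedance rate and correlation 0.5, the missed share runs from 2.2% if 5% of visits hold two values to 31% if all do.

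For ECG, the direction of the bias follows from the rule alone. Its size depends on the assumed abnormal-reading rate and correlation. At a 10% rate and one visit it runs from 27% up against 0.07% down (independent) to 5.5% against 0.06% (intraclass correlation 0.8). It concerns only the categorical interpretation in discordant triplicates, since the numeric ECG descriptive statistics, QTc included, use averages on both sides.

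The consequence is confined to descriptive safety tables. No efficacy result depends on either rule. A correction is still worth making, because the two rules err in opposite directions in different tables and so do not offset each other.

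**What to change.** **Laboratory and vital signs.** State in SAP 17.3 that the last-value rule applies only to by-visit descriptive summaries. Every post-baseline value (scheduled, unscheduled and same-visit repeat) should enter the maximum/minimum, shift-to-worst and worst-CTCAE-grade outputs. Remove the withdrawn vital-sign shift table from SAP 11.3 at the same time.

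**ECG.** Use one triplicate rule for the overall interpretation at baseline and afterwards, for example the worst or the majority reading. With three interpretation categories, the middle of the three readings serves as the majority. If the sponsor prefers to keep best-against-worst as a sensitive screen, place the symmetric table beside it and footnote the rule.

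**Cost.** A few SAP sentences and minor programming, with no new data. Somewhat more high-grade laboratory values and fewer ECG shifts would be reported. Worst of three at baseline can mask some real worsening. A majority rule masks less at baseline but can miss a single truly abnormal tracing after dosing. Upward shift from taking the worst over several visits remains under any triplicate rule and should be noted under the table.
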